#### **Study Visit Windows**

For BM data the assignment of data to each week (1, 2, 3 and 4) will be calculated from the date and time of the morning dose on Day 1. If no morning dose was taken on Day 1, then the date of Day 1 will be used and the time of the first recorded morning dose will be used. Weeks will be calculated as 168-hour intervals starting from this time. Note that any diary entries prior to this will be assigned to the screening period. Where missing dates or times do not allow the assignment of diary data to a treatment period (Screening or double blind) then it will be assumed that all data in the Screening booklet was recorded during Screening and all data in the remaining booklets were recorded after the booklets were provided to subjects. Abdominal symptom assessments will be assigned to the week as recorded in the diary. PAC-QOL is assessed at Day -1, Week 2 (Day 15) and Week 4 (Day 29). PAC-QOL assessments will be assigned to the time point relating to the visit at which they are recorded, regardless of actual study day. Assessments conducted at an Early Termination Visit will be assigned to the next scheduled visit that would have taken place if the subject had not discontinued, e.g. if the subject withdraws prior to Week 2 then the Early Termination Visit assessment will map to Week 2, whereas if the Early Termination Visit occurs after Week 2 then the assessment will be assigned to Week 4.

	Sc	creening	Double Blind Treatment Period				
Study Day/Week	Screening	Randomization	First Dose	Week 1	Week 2	Final Visit / Early Termination Visit Week 4	Follow-up Phone Contact
Visit Number:	1	2	-	3	4	5	-
Day	-15	-1	1	8	15	29	43

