# 13.1.3.1 Primary Endpoint

The primary endpoint for the study is the frequency of SBM at Week 1. An SBM is defined as any BM that does not occur within 24 hours after rescue medication use. The SAP will contain more details on the handling of rescue medication and missing or partial data.

In order to adjust for early withdrawals, weekly SBM frequency rates will be calculated as follows:

(Number of SBMs / Number of Days) 
$$\times$$
 7

The number of days in the denominator above is the number of days during the week that the subject was in the study. Weeks will be calculated as 168-hour intervals starting with the exact time of the first intake of study drug. The number of days will generally be 7 unless a subject drops out during a treatment week. If the number of days is less than 4, then the data will be considered insufficient and the rate will be set to missing.

The primary endpoint will be analyzed using van Elteren's test stratified by center to examine the difference between lubiprostone and placebo. Additionally the endpoint will be analyzed using analysis of variance (ANOVA) models with center and treatment in the model as a sensitivity analysis. The estimated least squares (LS) means, related mean difference and associated 95% CI will also be presented to aid interpretation of the clinical effect. The interaction between treatment and center will also be examined in a separate ANOVA model.

This endpoint will be analyzed for the FAS. A sensitivity analysis using the PP will also be presented.

To examine the effects of any dose reduction in response to an AE an additional sensitivity analysis will also be performed. This will be performed on the FAS where data from those subjects with a dose reduction will be excluded from the time of dose reduction and subjects will be treated as a drop-out from this time point onwards. Additionally, another factor will be added to the ANOVA model to examine the effect of dose reduction, this will be performed on the FAS, with no subjects excluded.

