## Appendix A Schedule of Study Procedures

	Screening	Randomization  Day -1 (a)	Treatment			Follow-up Period	
Study Day/Week	Day -15		First Dose Day 1 (b)	Week 1	Week 2	Final Visit or Early Termination Visit Week 4 (c)	Follow-up Phone Contact Week 6 (0)
Visit Windows (Days): (+/- 2 days)	-15 to -1	-1	1	8	15	29	43
Visit Number:	1	2	N/A	3	4	5	N/A
Informed consent	X						
Demographics and medical history (d)	X						
Inclusion/exclusion criteria (e)	X	X					
Medication history	X						
Physical examination	X					X	
Vital signs (f)	X	X				X	
Weight and height (g)	X					X	
Concomitant medications	X	X	X	X	X	X	X
Concurrent medical conditions	X						
Clinical laboratory tests (h)	X					X	
Pregnancy test (i)	X	X				X	
Urine drug screen	X						
Access IWRS for Subject ID/MED ID/Subject Status	X	X				X	
Dispense investigational drug		X					
Distribute rescue medications prescription as necessary	X	X		X	X		
Drug return/accountability/compliance				X	X	X	
Dispense study diary	X	X		X	X		
Efficacy:		ı				ı	I
Abdominal symptom assessment review (by diary)		X		X	X	X	
PAC-QOL		X			X	X	
Use of rescue medication (by diary)		X		X	X	X	
Diary-keeping by subjects (j)	X	X	X	X	X	X	
Diary collection/ compliance check (k)		X		X	X	X	
Safety:	 						
Guidance on avoidance of pregnancy and ova donation	X	X		X	X	X	
Pretreatment adverse events (1)	X	X					
Adverse events (m)			X	X	X	X	X
Dose reduction (optional) (n)				X	X		
Phone interview							X
	 			 	 		

Footnotes are on last table page.

N/A= not applicable.

- (a) Subjects will be randomized on Day -1, the last day of the Screening Period. They will also receive their bottle of dispensed investigational study drug on Day -1, although they will be instructed to take the first dose the next day, on Day 1.
- (b) Day 1 is the first day of study drug administration. Subjects are to take 1 capsule of lubiprostone 24 μg or placebo with 240 mL of water in the morning with breakfast, and again in the evening with dinner. Repeat this regimen for 4 weeks.
- (c) Conduct Final Visit procedures for subjects discontinued early per Section 7.6. Subjects who withdraw prematurely should return within 1 week of discontinuation for an Early Termination Visit.

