7.8.1 Primary Efficacy Endpoint(s)

The primary efficacy endpoint is SBM frequency at Week 1; an SBM is defined as any BM that does not occur within 24 hours after rescue medication use. Since rescue medication use will be disallowed during Week 1, the SBM frequency should equal the BM frequency. In the case of protocol violators, the analysis will be based on SBMs.

In order to adjust for early withdrawals or those with less than 7 days diary data, weekly SBM frequency will be calculated as follows:

7 x (Number of SBMs / Number of days)

Where the number of days is the number of days during the week that the subject was in the study. Weeks will be calculated as 168-hour intervals starting from the day after randomization (Day1), if there is no time recorded for the morning dose on Day1 then the time of the first recorded morning dose will be used. The number of days will generally be 7 unless a subject drops out during a treatment week. If the number of days is less than 4, then the data will be considered insufficient and the frequency will be missing.

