## Proportion of subjects with an SBM within 24 hours after first dose

The 24 hour period will be taken from the time of the first recorded dose in the patient diary. If the efficacy data is missing for the first 24 hours following this dose then it will be assumed that the patient did not experience any BM (including SBMs) during this period, this is based on the assumption that a patient is more likely to complete the diary on any particular day if they experience a BM than if they did not. The proportion of subjects with an SBM within 24 hours after first dose in Week 1 will be analyzed by a Cochran-Mantel-Haenszel (CMH) test stratified by center. Additionally a logistic regression model will be used with treatment and center as factors as a sensitivity analysis. The estimated odds ratio and associated 95% CI for both methods will be presented to aid interpretation of the clinical effect.

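### When the Day 1 morning dose is not taken, the SAP starts Week 1 before the first intake, contrary to the protocol; the effect on the trial result is very small

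*SAP*

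**What the plan says.** - **Protocol 13.1.3.1 (Primary Endpoint):** "Weeks will be calculated as 168-hour intervals starting with the exact time of the first intake of study drug". The weekly rate is the SBM count divided by days in the study that week, times 7.
- **SAP 7.1 (Study Visit Windows):** assignment of bowel-movement data to weeks "will be calculated from the date and time of the morning dose on Day 1". If that morning dose was not taken, "then the date of Day 1 will be used and the time of the first recorded morning dose will be used". The section adds: "Note that any diary entries prior to this will be assigned to the screening period". Entries after the constructed start therefore belong to Week 1, whether or not a dose had yet been taken.
- **SAP 7.8.1:** "Weeks will be calculated as 168-hour intervals starting from the day after randomization (Day1" (the bracket closes after the quoted words). Here the clock time is borrowed when no time was recorded for the Day 1 morning dose, which is a different trigger from the one in 7.1.
- **SAP 7.8.2 (SBM within 24 hours):** "The 24 hour period will be taken from the time of the first recorded dose in the patient diary".
- **SAP 7.8 (diary baseline):** the 14 baseline days are counted back from the day of first dose.
- **Protocol Appendix A, footnote (b):** "Day 1 is the first day of study drug administration". The visit table in SAP 7.1 likewise labels Day 1 as the first dose.
- **SAP 7.13:** describes the SAP as adding detail and further analyses. It does not mention a changed week definition.

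**The concern.** Time zero for the primary endpoint differs between the two documents. Under the protocol it is an observed event, the first intake. Under the SAP fallback it is a composite: the date of Day 1 joined to a clock time taken from a later day. When the Day 1 morning dose was not taken, that composite falls before any drug was taken.

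Three things follow for such a subject. Untreated hours enter Week 1, and the same number of hours at the end of the true first treated week moves into Week 2. The denominator does not correct for this, because it counts days in the study rather than days on drug. The 24-hour endpoint runs from the true first dose, so two efficacy endpoints for the same subject use different clocks.

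At stake is an undeclared change in how the primary endpoint is derived. It lowers the Week 1 value of affected subjects, by more on active drug than on placebo if lubiprostone works as planned.

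**Working it through.** **1. The plan's own figure.** Inputs from SAP 6.0: means 5.9 and 4, SDs 4 and 2.7, two-sided alpha 0.05, power 90%, 1:1 allocation.
- Common SD = √((2.7² + 4²)/2) = √11.645 = 3.412; difference = 1.9.
- A two-sample t-test needs 69 per arm. Dividing by the Wilcoxon efficiency 3/π gives 69 × π/3 = 72.3, so 73 per arm and 146 in total. This matches the stated 146.
- Power at 146 by this method is about 90.4%. That is the reference value below.

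**2. Which subjects the fallback reaches.**
- *First dose on the evening of Day 1.* No morning dose was taken on Day 1, so SAP 7.1 applies. Week 1 starts at a morning clock time on Day 1, some hours before the first dose. This holds under either meaning of Day 1.
- *First dose on a later day.* This arises only if Day 1 is the day after randomization (SAP 7.8.1). If Day 1 is the first day of administration (protocol Appendix A), it cannot occur.
- *Overlap with baseline.* In the later-day case, baseline is counted back from the day of first dose while Week 1 starts on Day 1, so the same days can fall in both.

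**3. Effect per affected subject.** Assumptions: 1.5 SBMs per week before the dose (the baseline median in protocol 4.1.4; the means in Table 4.a run from 1.28 to 1.68), and a constant rate after it of 5.9 (active) or 4 (placebo). The gap lengths are also assumed.

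Loss in Week 1 = (hours/24) × (on-treatment rate − 1.5)/7.

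| Gap | Active | Placebo | Condition |
|---|---|---|---|
| 10 h | (10/24) × 4.4/7 = 0.26 | (10/24) × 2.5/7 = 0.15 | either meaning of Day 1 |
| 24 h | 4.4/7 = 0.63 | 2.5/7 = 0.36 | Day 1 = day after randomization |
| 48 h | 2 × 4.4/7 = 1.26 | 2 × 2.5/7 = 0.71 | Day 1 = day after randomization |

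The pre-dose rate cancels from the treatment difference among affected subjects, which is 1.9 × (1 − hours/168): 1.76 at 12 h, 1.63 at 24 h and 1.36 at 48 h.

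**4. Effect on the trial.** The documents give no share of affected subjects, so a range is assumed, equal in both arms and with SDs unchanged. Difference = 1.9 × (1 − share × hours/168), for gaps of 12 to 24 h.

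| Share affected | Difference | Power at 146 |
|---|---|---|
| 0% | 1.900 | 90.4% |
| 1% | 1.897–1.899 | 90.3–90.4% |
| 5% | 1.886–1.893 | 90.0–90.2% |
| 10% | 1.873–1.886 | 89.6–90.0% |
| 20% | 1.846–1.873 | 88.7–89.6% |

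With a 10 h gap and 5% affected, the difference changes by 0.05 × 1.9 × 10/168 = 0.006 SBM.

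**The case against.** The strongest reply is that this hardly matters. Subjects are told to start on the morning of Day 1 (protocol 6.1, 7.4, 8.1.3 and 9.3.2), so few should meet the fallback. The rule is the same in both arms, and dilution toward no difference creates no evident false-positive risk unless late starts differ by arm. The constant-rate assumption may also overstate the loss: the hours displaced are the last of the true first week, and if the response is front-loaded they carry fewer SBMs. All of this stands, and it limits the point to a minor one.

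A second reply is that a clock tied to the scheduled start suits a full analysis set that keeps randomized subjects whether or not they were treated. That is defensible, but the SAP does not argue it, and SAP 7.13 does not declare it.

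A third is that SAP 7.8.1 only imputes a missing clock time, which is reasonable. Read alone, it could be that. But SAP 7.1 is triggered by a dose not taken, so the two sections do not state the same rule.

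A reader might also infer that the SAP ignores a complete absence of dosing on Day 1 and so routinely counts a day or more of untreated time. The text does not support this: the trigger is a missed morning dose, the case that certainly arises is an evening start, and full-day gaps depend on an unsettled definition of Day 1. Nor are the differing clocks a fault in the 24-hour endpoint, which properly runs from the actual first dose.

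**Conclusion.** The contradiction is real and undeclared. For a subject whose first dose is on the evening of Day 1, the SAP counts pre-dose hours in the primary endpoint and the protocol does not. Losses of a day or more are conditional on reading Day 1 as the day after randomization.

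The stronger conclusion, that the primary result or the sample size is at risk, is not supported. At an assumed 5% affected with gaps of 12 to 24 hours, power changes by less than half a percentage point, and even at 20% with a 24-hour gap it is 88.7%. These figures rest on an assumed share, equal late starting by arm, a step change to a constant rate at first dose, and unchanged SDs. The reason to act is that the time zero of the primary endpoint should be stated once, agree with the protocol, and be settled before unblinding.

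**What to change.** - In SAP 7.1 and 7.8.1, define time zero as the date and time of the first recorded intake, morning or evening.
- Impute only a missing clock time, and place it on the actual date of first intake. State one trigger in both sections.
- Use the scheduled Day 1 start only for full-analysis-set subjects who never dosed. They have no intake time under the protocol rule, and no recorded morning dose to borrow from under the present SAP rule, so the SAP should also state a nominal clock time for them.
- Align the baseline window in SAP 7.8 and the 24-hour endpoint in SAP 7.8.2 to the same time zero, so that no diary day counts in both baseline and Week 1.
- If the sponsor prefers the scheduled clock, declare and justify it in SAP 7.13 and add a sensitivity analysis using the protocol's start.

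Cost: a few sentences in the SAP and one derivation line in the program. The diary already asks for the date and time of each dose, and the sample size does not change.

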# 7.2 ANALYSIS SETS

Total Set: The total set consists of all subjects who signed the informed consent form, including subjects withdrawn prior to randomization.

Full Analysis Set (FAS): This will consist of all subjects randomized to receive study treatment whether or not they received treatment. Subjects will be reported according to their randomized treatment group regardless of treatment received.

Per-Protocol Analysis Set (PPS): The PPS will consist of subjects in the FAS with the additional following criteria for exclusion:

- Did not receive study treatment as per randomization schedule (including not receiving any randomized treatment)
- Dose of randomized treatment was adjusted.

CROSS-REGIONAL TEMPLATE				
Template Number:	C-TMPL-DO-801	Page:	14 of 31	
Version Number:	1.2	Effective Date:	14 Sep 2015	
This version replaces	s: 1.1			
Parent Document:	C-SOP-DO-800			
Template Title:	Statistical Analysis Plan (Legacy Takeda)			

- Violated inclusion criteria, such as:
  - Does not have a history of constipation defined as SBM frequency of less than 3 times per week on average for 6 months or longer (and observed during Screening Period).
  - Does not have SBMs with  $\geq 1$  of the following 3 symptoms for the last 6 months or longer, in at least 1 out of every 4 bowel movements: scybalum stool or hard feces, straining, or the sensation of incomplete evacuation.
  - The subject rarely has loose stools without the use of laxatives.
- Violated exclusion criteria, such as:
  - The subject has a history or clinical manifestations of significant mechanical obstruction (intestinal obstruction due to tumor, hernia etc).
  - Has chronic constipation due to a secondary cause (medications, diabetes mellitus, hypothyroidism, depression, etc).
  - Has sufficient criteria for IBS or there is a functional defecation disorder.
  - BM frequency is 3 or more per week.
  - SBM frequency has been less than 3 times per week for less than 6 months in duration or whose symptoms associated with SBM have been present for less than 6 months (hard feces, sensation of incomplete evacuation, or straining).
  - Received treatment with a rescue medication within 24 hours prior to the first dose on the morning of Day 1.
  - Has megacolon/megarectum or has received a diagnosis of intestinal pseudoobstruction.
  - Has confirmed or suspected organic disorders of the large intestine (obstruction, stenosis, carcinoma, or inflammatory bowel disease). Any subject in whom total colonoscopy has detected a polyp requiring treatment is excluded from this study.
  - Has been hospitalized for gastrointestinal or abdominal surgery within 3 months before the start of this study.
  - Use of any excluded medications, procedures or treatments prior to the assessment of the primary endpoint.

Any other significant event interfering with efficacy evaluation of primary endpoint, to be decided at the Targeted Data Review Meeting, for example,. Definitions of criteria constituting major deviations will be provided, prior to unblinding.

Therefore subjects will be reported according to their treatment group.

CROSS-REGIONAL TEMPLATE				
Template Number:	C-TMPL-DO-801	Page:	15 of 31	
Version Number:	1.2	Effective Date:	14 Sep 2015	
This version replaces:	1.1			
Parent Document:	C-SOP-DO-800			
Template Title: S	tatistical Analysis Plan (Legacy Takeda)			

Safety Analysis Set (SAF): This will consist of all subjects who receive study treatment. Subjects will be assigned to the treatment group according to the actual treatment received.

The FAS will be used for efficacy analyses. Supportive analyses based on the PP will be performed for the primary efficacy variable. The SAF will be used for all safety analyses.

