#### Per-Protocol Analysis Set

The Per-Protocol (PP) population will consist of subjects in the FAS with the additional following criteria for exclusion:

- Did not receive study treatment as per randomization schedule.
- Dose of randomized treatment was not adjusted.
- Violated inclusion criteria, such as:
  - Does not have a history of constipation defined as SBM frequency of less than 3 times per week on average for 6 months or longer (and observed during Screening Period).
  - Does not have SBMs with ≥1 of the following 3 symptoms for the last 6 months or longer, in at least 1 out of every 4 bowel movements: scybalum stool or hard feces, straining, or the sensation of incomplete evacuation.
  - The subject rarely has loose stools without the use of laxatives.
- Violated exclusion criteria, such as:
  - The subject has a history or clinical manifestations of significant mechanical obstruction (intestinal obstruction due to tumor, hernia etc).

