# Sensitivity Analyses

The primary analysis as described above will be repeated using the PP rather than the FAS. An additional sensitivity analysis using the FAS assuming a 'worse-case' scenario approach will also be conducted, where missing values, including those with < 4 days diary data, are assigned the worst case values (the lowest SBM frequency for week 1) recorded in the study by any subject for that endpoint at that time.

Additionally the endpoint will be analyzed using robust analysis of variance (ANOVA) models (by M-estimation [3] using PROC ROBUSTREG in SAS) with center and treatment in the model as a sensitivity analysis using the FAS. The interaction between treatment and center will also be examined in a separate model, using robust ANOVA methods as previously described.

To examine the effects of any permanent dose reduction in response to an AE (as recorded on the eCRF) an additional sensitivity analysis will also be performed. This will be performed on the

CROSS-REGIONAL TEMPLATE			
Template Number:	C-TMPL-DO-801	Page:	22 of 31
Version Number:	1.2	Effective Date:	14 Sep 2015
This version replaces:	1.1		
Parent Document:	C-SOP-DO-800		
Template Title: St	tatistical Analysis Plan (Legacy Takeda)		

FAS where data from those subjects with a dose reduction will be excluded from the time of dose reduction (taken as date of last BID dose + 12 hours, e.g. if the evening dose is removed then the time will be from the morning dose + 12 hours, if the morning dose is removed then it will be from the previous day's evening dose + 12 hours) and subjects will be treated as a dropout from this time point onwards. This will be implemented using robust ANOVA. Additionally, another factor will be added to the robust ANOVA model to examine the effect of dose reduction (), this will be performed on the FAS. This analysis will not be carried out if the number of subjects with a dose reduction within the first week is less than 5%.

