#### 7.8.2 Secondary Efficacy Endpoint(s)

The interaction of treatment and center and the effect of dose reduction will not be examined for any secondary endpoints. All secondary endpoints will be analyzed for the FAS only.

SBM frequency at Week 2, 3 and 4

The secondary endpoint will be analyzed as specified for the primary endpoint separately for each week.

Additionally for patients with a missing Week 2 frequency estimate (where diary days < 4 in Week 2) the Week 1 estimate will be carried forward, if available. For the worse-case analysis all missing Week 2 values will be assigned the lowest SBM frequency for week 2.

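### The per-protocol set drops every dose-adjusted subject with no time limit, so a reduction after Week 1 discards a valid full-dose Week 1 value from the only endpoint that set serves

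*SAP*

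**What the plan says.** SAP 7.2 defines the PPS as the FAS less subjects who meet any of a list of exclusions. One of these is "Dose of randomized treatment was adjusted", without reference to when. Protocol 13.1.1 has the same item, also untimed and with its sense reversed: "Dose of randomized treatment was not adjusted". Another item in the SAP list does carry a limit: "Use of any excluded medications, procedures or treatments prior to the assessment of the primary endpoint".

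The PPS has one use. SAP 7.2 states "Supportive analyses based on the PP will be performed for the primary efficacy variable", and SAP 7.8.1 adds "The primary analysis as described above will be repeated using the PP rather than the FAS". For Weeks 2 to 4 and the other secondary variables, SAP 7.8.2 states "All secondary endpoints will be analyzed for the FAS only".

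Protocol 7.7 allows dose reduction for adverse events throughout the double-blind period, including between visits. Appendix A marks optional dose reduction at the Day 8 and Day 15 visits. Protocol 6.1 and SAP 4.2 also let the investigator weigh bowel movement frequency and consistency when deciding to reduce.

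**The concern.** A per-protocol analysis of Week 1 should ask whether the result holds among subjects who followed the protocol up to the end of Week 1. The dose criterion looks beyond that point. It removes a complete full-dose Week 1 observation because of something that happened in Weeks 2 to 4.

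The loss need not be neutral. If investigators tend to reduce the dose in subjects with frequent bowel movements, high Week 1 counts are removed selectively. Under the planning assumptions such subjects are more common on lubiprostone, so blinded decisions would still take more of them from that arm and pull the per-protocol difference toward zero. The PPS result could then look weaker than the FAS result, or disagree with it, for a reason unrelated to Week 1 adherence.

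**Working it through.** **Timing.** Week 1 is the 168 hours from the Day 1 morning dose, so it ends on the morning of Day 8. Visit 3 is Day 8 with a 2-day window (Protocol 9.3), that is Days 6 to 10. Among scheduled visits, only a Visit 3 on Day 6 or 7 puts a reduction clearly inside Week 1. A reduction at Visit 4 (Day 15) is always after it. Reductions between visits can fall on either side.

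**Planning base.** Inputs from SAP 6.0: means 4 and 5.9, SDs 2.7 and 4, two-sided alpha 0.05, power 90%.

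- Pooled SD = sqrt((2.7² + 4²)/2) = sqrt(11.645) = 3.41.
- The two-sample t-test for a difference of 1.9 needs 68.76 per arm.
- Dividing by the Wilcoxon efficiency 3/π gives 68.76 × 1.0472 = 72.01, rounded up to 73 per arm, or 146 in total. This matches the SAP.

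**Loss of numbers alone.** Noether's approximation uses p = Φ(1.9/sqrt(2.7² + 4²)) = Φ(0.394) = 0.653 and power = Φ(sqrt(12·n₀n₁/(n₀+n₁))·(p − 0.5) − 1.96).

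- 73 and 73: sqrt(12 × 36.5) = 20.93; 20.93 × 0.1531 = 3.20; Φ(3.20 − 1.96) = 0.893.
- Assumed loss of 4, 7, 11 or 15 lubiprostone subjects (5, 10, 15 or 20% of 73): 0.885, 0.878, 0.867, 0.854.

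**Loss related to outcome.** The documents give neither the rate of reduction after Week 1 nor its relation to Week 1 frequency, so both are assumed. The simulation used:

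- 4000 trials for each of gamma and negative binomial Week 1 counts, with the SAP means and SDs;
- 75 per arm in 10 equal centres (assumed);
- the van Elteren test with tie correction, two-sided 0.05;
- removal of k subjects reduced after Week 1.

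Simulation error on a power near 0.85 is sqrt(0.85 × 0.15/4000) = 0.006. Pairs of figures are gamma / negative binomial.

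| Which subjects are removed | k | Difference | Power |
|---|---|---|---|
| None | 0 | 1.90 / 1.90 | 0.867 / 0.850 |
| From the top 30 of 150, arms pooled | 2 | 1.84 / 1.84 | 0.849 / 0.828 |
| | 4 | 1.78 / 1.78 | 0.836 / 0.808 |
| | 8 | 1.65 / 1.65 | 0.789 / 0.756 |
| From the top 15 of 75 on lubiprostone only (extreme) | 2 | 1.73 / 1.73 | 0.814 / 0.793 |
| | 4 | 1.55 / 1.56 | 0.758 / 0.725 |
| | 8 | 1.15 / 1.17 | 0.589 / 0.543 |
| At random | 2 to 8 | 1.90 | 0.83 to 0.87 |

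In the pooled scenario 72 to 74% of those removed were on lubiprostone, although treatment played no part in the choice.

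A second illustration used gamma counts and a correlation of 0.3 to 0.5 between Week 1 frequency and later reduction, in the lubiprostone arm only. The PPS lubiprostone mean falls from 5.9 to 5.76-5.65 at 5% late reducers, 5.66-5.48 at 10% and 5.56-5.32 at 15%. At zero correlation it does not move.

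The 0.893 and the 0.85-0.87 are different base powers because the sample sizes, data models and tests differ. Compare each only with its own reduced values.

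**The case against.** The case for leaving the rule alone has five parts.

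- **No decision turns on the PPS.** Both documents call it supportive, the bias runs toward zero and so cannot create a false claim, and SAP 7.3 tabulates reasons for exclusion. This stands and limits the importance of the point.
- **SAP 7.8.1 already handles dose reduction properly elsewhere.** Its sensitivity analysis on the FAS drops data only from the time of reduction, so it keeps the Week 1 value of anyone reduced later. That is true, but it is a robust ANOVA on another set and does not repair the PPS. The SAP also attaches a waiver for fewer than 5% reductions within the first week. It does show that the SAP recognises timing elsewhere.
- **Blinded review could settle the timing.** SAP 7.2 promises definitions of major deviations before unblinding and refers other interfering events to the Targeted Data Review Meeting. As written, that meeting can add exclusions; nothing re-admits a subject who meets a listed one.
- **The size rests on unknowns.** Most of the reduction text concerns adverse events, the schedule entry is optional, and the share of reductions after Week 1 is not known. This is correct. The largest losses need eight reductions, all on lubiprostone and all among its highest counts, which is an outer bound.
- **A four-week regimen could justify a four-week definition of adherence.** That would be reasonable if the PPS served four-week endpoints, but it serves none.

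**Conclusion.** The point holds. Applied as written, the criterion removes valid full-dose Week 1 values because of later events, from a set whose only purpose is the Week 1 analysis.

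The size depends on a reduction rate that the documents do not give. Under blinded selection from the pooled top 20%, two to eight late reductions (1.3% to 5.3% of 150) lower the difference by 0.06 to 0.25 SBM per week, or 3% to 13% of 1.90. With selection unrelated to frequency there is no bias and little loss of power. The primary FAS test and all secondary analyses are untouched. This should be corrected, but it does not threaten the trial's main conclusion.

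**What to change.** In SAP 7.2, extend "Dose of randomized treatment was adjusted" with the clause: before the end of Week 1 (168 hours after first dose). Reductions inside Week 1 still exclude; later ones do not. Time the reduction by the rule already in SAP 7.8.1, "taken as date of last BID dose + 12 hours". In Protocol 13.1.1, first remove the word 'not' from the criterion so that it excludes subjects whose dose was changed, then add the same clause.

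The cost is a wording change in two documents before unblinding, plus one data check. The SAP 7.8.1 timing rule is written for permanent reductions due to adverse events recorded in the eCRF, whereas Protocol 6.1 sends dose adjustments to source notes. Confirm that the dates of reductions made for bowel frequency are in the eCRF or can be taken from the dose times in the diary (Protocol Appendix E), and state that the 12-hour rule applies to them too.
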